4.5.5 Study/project specific programming

The standard analysis programs need to be adapted for each study/project.

4.5.6 Censoring reason

In order to summarize the various reasons for censoring, the following categories will be calculated for each time to event variable based on the treatment completion page, the study evaluation completion page and the survival page.

For survival the following censoring reasons are possible:

[figure not shown]
- Alive
- Lost to follow-up

For PFS and TTP (and therefore duration of responses) the following censoring reasons are possible:

- Ongoing without event
- Lost to follow-up
- Withdrew consent
- Adequate assessment no longer available*
- Event documented after two or more missing tumor assessments (optional, see [Table 3-2](#))
- Death due to reason other than underlying cancer
- Initiation of new anti-cancer therapy

* Adequate assessment is defined in [Section 3.2.7](#). This reason is applicable when adequate evaluations are missing for a specified period prior to data cut-off (or prior to any other censoring reason) corresponding to the unavailability of two or more planned tumor assessments prior to the cut-off date. The following clarifications concerning this reason should also be noted:

- This may be when there has been a definite decision to stop evaluation (e.g. reason="Sponsor decision" on study evaluation completion page), when patients are not followed for progression after treatment completion or when only UNK assessments are available just prior to data cut-off).
- The reason "Adequate assessment no longer available" also prevails in situations when another censoring reason (e.g. withdrawal of consent, loss to follow-up or alternative anti-cancer therapy) has occurred more than the specified period following the last adequate assessment.
- This reason will also be used to censor in case of no baseline assessment.

5 References (available upon request)

Dent S, Zee (2001) application of a new multinomial phase II stopping rule using response and early progression, *J Clin Oncol*; 19: 785-791.

Eisenhauer E, et al (2009) New response evaluation criteria in solid tumors: revised RECIST guideline (version 1.1). *European Journal of Cancer*, Vol.45: 228-47.

[figure not shown]
Ellis S, et al (2008) Analysis of duration of response in oncology trials. *Contemp Clin Trials* 2008; 29: 456-465.

FDA Guidelines: 2005 Clinical Trial Endpoints for the Approval of Cancer Drugs and Biologics, April 2005.

FDA Guidelines: 2007 Clinical Trial Endpoints for the Approval of Cancer Drugs and Biologics, May 2007.

14.2 Appendix 2: International Neuroblastoma Response Criteria (INRC)

Table 14-1 INRC definition

RESPONSE	ANATOMICAL IMAGING + MIBG (PET)
CR	
• Complete resolution of non-primary measurable lesions• MIBG non-avid (no increased FDG-PET uptake for mIBG non-avid tumors) of non-primary lesions
PR	
• 30% decrease in size/sum of non-primary measurable disease (RECIST), or• $\geq 50\%$ reduction in MIBG score (Relative MIBG score ≥ 0.1 to ≤ 0.5)
PD	
• Any new lesion by CT/MRI or MIBG• $>20\%$ increase in size AND a minimum absolute increase of 5 mm in longest dimension in existing lesions• Relative mIBG (FDG-PET for mIBG non-avid tumors) score ≥ 1.2
SD	Neither sufficient shrinkage for MR or PR nor sufficient increase for PD

Table 14-1 describes Revised International Neuroblastoma Response Criteria written by Park J, Valteau-Couanet D, Baruchel S et al. (manuscript in preparation)

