All patients will be required to provide archival tumor biopsies (at diagnosis or relapse) unless otherwise agreed upon by Novartis and the investigator. At screening, all patients with neuroblastoma will undergo bilateral bone marrow aspirates (BMA) and/or biopsy and will be examined for presence of disease per standard institutional practice. Patients with bone marrow involvement at study entry will have repeat bone marrow evaluations for disease response at periodic intervals during the study. If feasible, pre- and post-treatment bone marrow samples (BMA and/or biopsy) will be collected from these patients. All patients with primary CNS tumors (including MRT) will be required to have a cerebrospinal fluid (CSF) sample drawn at screening and examined for presence of tumor cells unless otherwise agreed upon by Novartis and the investigator. Patients with CSF positive for disease at screening will require a repeat CSF examination for confirmation of Complete Response (CR). If CSF is collected as part of efficacy assessment or if CSF is collected as part of routine/standard care at any time after patient has received first dose of LEE011, a sample will be requested for testing LEE011 levels in the CSF. If feasible, a PK blood sample corresponding to the timing of CSF collection will also be requested.

Patients will continue to receive treatment with LEE011 until disease progression, occurrence of unacceptable toxicity that precludes any further treatment, or if treatment is discontinued at the discretion of the investigator or by patient's withdrawal of consent. All patients will have an EOT visit within 14 days of permanently discontinuing LEE011 and will be followed for 30 days after last dose of study treatment. Analysis of the study data may occur after all patients have had the opportunity to complete at least 6 cycles of treatment.

Approximately 64 patients will be treated in the entire study.

Figure 4-1 Overview of study design

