Subsequent tumor evaluations will be performed on Day 22 (± 7 days) of cycles 2, 4 and 6. After cycle 6 tumor evaluations will be performed on Day 22 (± 7 days) of every 4th cycle (e.g., C10, C14, C18), or sooner if there is clinical evidence of disease progression. Tumor evaluations will also be performed at EOT. If the last prior tumor evaluation was within 28 days of EOT or objective evidence of progressive disease has already been documented, then tumor evaluations do not need to be repeated at EOT.

Tumor evaluations after the screening assessment will include evaluation of all sites of disease identified at baseline, using the same technique that was used at screening. If there was no evidence of disease in a body region at screening, that region does not need to be imaged at subsequent assessments, unless there is clinical concern for a new lesion in that body region. Bone marrow aspirate and/or biopsies and MIBG scans are not required after baseline if they were negative at screening.

The CSF test is required for primary CNS tumors (including MRT) patients at screening and is performed per institutional standards. If sampling is not feasible, patients may still enroll in study after discussion with Novartis and the investigator. Information will be collected if performed. CSF will be performed at Screening and if positive at screening, subsequent measurements are performed only for confirmation of CR as needed on Day 22 (± 7 days) of cycles 2, 4 and 6. After cycle 6 tumor evaluations, CSF test will be performed as needed on Day 22 (± 7 days) of every 4th cycle (e.g., C10, C14, C18), or sooner if there is clinical evidence of disease progression. Only 2 negative sequential CSF cytology are required for establishing CR.

All radiological assessments obtained for all patients enrolled during the study will be centrally collected and subjected to quality checks by an imaging CRO selected by Novartis. The site manual provided by the designated imaging CRO will provide further details regarding image collection.

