10.5.4 Efficacy evaluation

Assessment of preliminary efficacy for all patients will be based on RECIST v1.1 ([Appendix 1](#)). In addition, patients with primary CNS tumors (including MRT) will have response assessment per RANO criteria ([Appendix 3](#)) whenever possible. Disease response in Neuroblastoma patients will additionally be assessed per INRC ([Appendix 2](#)).

TTP and DOR per RECIST v1.1 will be presented descriptively for the neuroblastoma and the MRT arms in the expansion phase using a Kaplan-Meier curve. Summary statistics from the Kaplan-Meier distribution will be determined, including the median and estimates at 4 and 8 months, for TTP and DOR respectively. These statistics will be provided as point estimates with 95% confidence intervals.

ORR as per RECIST v1.1 will be presented at the MTD/RDE as point estimate and corresponding 95% exact confidence interval according to Clopper-Pearson for the neuroblastoma and the MRT population separately.

The same analysis will also be presented as per RANO in MRT patients and as per INRC in Neuroblastoma patients.

Moreover, preliminary efficacy response as per RECIST 1.1 will be listed for all patients as well as preliminary efficacy response per RANO and INRC for patients with Primary CNS and with Neuroblastoma, respectively.

Any other additional analysis will be fully specified in the RAP.

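### The INRC table lets a neuroblastoma patient with an unchanged primary and positive marrow count as a complete responder, and gives a primary-only patient no CR and no PR by size

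*Protocol*

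**What the plan says.** Protocol Table 3-1 lists INRC response for neuroblastoma under the third secondary objective. Section 10.5.4 gives ORR per RECIST 1.1 with an exact 95% interval and adds: "The same analysis will also be presented as per RANO in MRT patients and as per INRC in Neuroblastoma patients".

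The INRC definition is Appendix 2, Table 14-1, which has one criteria column, for anatomical imaging and MIBG (PET).

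- CR has two bullets: "Complete resolution of non-primary measurable lesions" and "MIBG non-avid (no increased FDG-PET uptake for mIBG non-avid tumors) of non-primary lesions".
- PR has two routes. The first is "30% decrease in size/sum of non-primary measurable disease (RECIST), or". The second is a 50% or greater "reduction in MIBG score (Relative MIBG score ≥ 0.1 to ≤ 0.5").
- PD is any new lesion, growth of existing lesions by more than 20% and at least 5 mm, or a relative MIBG score of 1.2 or more.
- SD is what remains. It refers to a category MR that the table does not define.

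On marrow, Section 4.1 states: "Patients with bone marrow involvement at study entry will have repeat bone marrow evaluations for disease response at periodic intervals during the study". Table 7-1 repeats a positive marrow at Cycles 2, 4 and 6 and every fourth cycle after that. Section 7.2.1 leaves the assessment of MIBG and marrow response to each site's usual practice. It gives no criteria for marrow and no rule for combining it with the INRC category.

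**The concern.** A response rate should not count as complete responders patients whose primary tumor has not changed or whose marrow is still positive. It should also be able to record a response in a patient whose only disease is the primary. Table 14-1 appears to fail on both counts. The protocol collects marrow specifically for response, and the table then makes no use of it.

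At stake is the INRC rate and its interval, and the patient-level INRC listing. The same patient can also carry conflicting labels. RECIST in Appendix 1 makes no distinction between primary and non-primary lesions, so an unchanged measurable primary blocks a RECIST CR while leaving an INRC CR open. No rule says how to read such a pair.

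**Working it through.** The plan gives no figure for this point, so the check applies each row of Table 14-1 to defined patients.

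**Step 1. Which rows are limited to non-primary lesions?**

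| Row | Limited to non-primary lesions | Uses marrow |
|---|---|---|
| CR, anatomical | yes | no |
| CR, MIBG/PET | yes | no |
| PR, anatomical | yes | no |
| PR, MIBG score | no | no |
| PD, new lesion | no | no |
| PD, growth | no | no |
| PD, MIBG score | no | no |

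**Step 2. Patient A: metastases cleared on CT/MRI and MIBG, primary unchanged, marrow positive at every repeat.** Both CR bullets are met. There is no new lesion, no growth and no rise in MIBG score, so no PD row applies. The table gives CR.

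**Step 3. Patient B: disease in the primary only, shrinking by 30% or more.** The anatomical PR row does not apply, because there is no non-primary disease to measure. The CR bullets do not apply either. Reading them as met because there is nothing to clear would make every primary-only patient CR from the first scan, which cannot be intended.

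- MIBG-avid primary: PR is available through the score, and SD and PD are available.
- MIBG non-avid primary: there is no baseline score to halve, so only SD and PD remain, even if RECIST gives PR.

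**Step 4. The MIBG PR line.** Take relative score as follow-up score divided by baseline score. This is an assumption, since the table does not define it. A 50% or greater reduction then means a relative score of 0.5 or less. The bracket allows only 0.1 to 0.5. A fall of more than 90% gives a relative score below 0.1, which meets the words and fails the bracket. If the score takes whole numbers (a second assumption, because no scoring system is named), 11 falling to 1 gives 1/11 = 0.091 and 21 falling to 2 gives 2/21 = 0.095. Neither is uptake-free. Under the bracket such a patient is PR only if the anatomical route applies, and SD is not a sensible label for a fall of that size.

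**Step 5. Does the protocol supply the missing rule elsewhere?** Section 7.2.1 ties CSF cytology to CR by asking for two sequential negative results. There is no counterpart for marrow.

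**Step 6. Scale.** One reclassified patient among n moves the rate by 100/n points. Section 10.8 plans about 18 patients per arm: 100/18 = 5.6. Exact 95% intervals at n = 18:

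| Responders | Rate | 95% interval |
|---|---|---|
| 0 | 0% | 0 to 18.5% |
| 1 | 5.6% | 0.1 to 27.3% |
| 2 | 11.1% | 1.4 to 34.7% |
| 3 | 16.7% | 3.6 to 41.4% |

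The documents do not say how many neuroblastoma patients were enrolled. For illustration, n = 5 gives 20 points per patient and n = 10 gives 10.

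**The case against.** The strongest reply is that the consequences are small and the picture incomplete. INRC is additional to RECIST, is applied where possible, and carries no hypothesis, power or decision rule. SAP Section 2.5.4 drops the expansion evaluation of anti-tumor activity because enrollment was halted. SAP Section 2.7 analyses no efficacy in the final CSR. The SAP refers repeatedly to the primary CSR analysis plan, which is not supplied and could define a combined response. The column heading and the undefined MR category suggest that the table may be the imaging part of a larger scheme, and a column lost in PDF reading cannot be fully excluded. The table is attributed to an external revision still in preparation, so rewriting it costs comparability.

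Most of this limits the size of the problem and does not remove it. If the table is only a component, the protocol does not say so, and Section 10.5.4 reports it as the INRC response. RECIST does not fully cover for it either. Inclusion criterion 6 admits neuroblastoma on a positive MIBG scan, and Appendix 1 cannot record a PR for a patient with no measurable lesion on imaging.

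A reader might infer four stronger things that the documents do not support:

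- That the table scores only non-primary lesions. PR by MIBG score and every PD row have no such limit.
- That a primary-only patient cannot be scored. PD, SD and, if avid, PR by MIBG are available.
- That some MIBG responses certainly have no category. The words and the bracket conflict, and one reading closes the gap.
- That PD in MIBG non-avid tumors depends on PET. A new lesion on CT/MRI and growth in size are separate PD criteria.

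**Conclusion.** The concern holds in limited form. By its own wording, Table 14-1 gives CR to a patient with an unchanged primary and persistent marrow disease. It denies CR and anatomical PR to a primary-only patient, and denies any PR if that patient is MIBG non-avid. It also contradicts itself on MIBG falls of more than 90%. This is a stated rule giving a wrong answer for a named secondary endpoint.

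It does not touch the primary objective. The effect is confined to the INRC results in the primary CSR for the neuroblastoma patients actually enrolled. The 5.6-point figure describes the planned 18-patient arm and is not an estimate of what happened; no document says how many patients are affected. The conclusion assumes that the table is complete as read and that the primary CSR analysis plan does not already supply a combining rule.

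**What to change.** 1. State an overall INRC rule. CR requires clearance of every component involved at baseline, including the primary and any marrow positive at screening. Apply the anatomical PR row to the primary as well.
2. Define MIBG PR as a relative score of 0.5 or less that does not meet CR, so that the range has no gap. The 0.5 limit is the table's own.
3. If the table is meant only as the imaging or metastatic component, label it so and do not report it as overall INRC response. This is the minimum change.

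The cost is appendix wording and a derivation program. No scan or aspirate is added: Section 7.2.1 already says "Tumor evaluations after the screening assessment will include evaluation of all sites of disease identified at baseline", and Table 7-1 already repeats positive marrows. The downside is that the INRC response rate may fall once patients with residual primary or marrow disease are no longer counted as CR. Comparability with the external source may also suffer, so the departure should be stated.

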4.3 Definition of end of the study

The study data will be analyzed and reported in the primary Clinical Study Report (CSR) taking into account all patients' data of the dose escalation and expansion parts up to the time when all patients continuing to receive treatment have completed at least six cycles of treatment with LEE011, all patients have discontinued from the study, the study is terminated early, or another clinical study that can continue to provide drug becomes available and all

[figure not shown]

4. Patients must meet the following hematologic criteria:
 - a. Peripheral absolute neutrophil count (ANC) $\geq 1000/\mu\text{L}$ without growth factor support within 7 days prior to first dose of LEE011
 - b. Platelet count $\geq 75,000/\mu\text{L}$ without platelet transfusions within 7 days prior to first dose of LEE011
 - c. Hemoglobin ≥ 8.0 g/dL without blood transfusions within 7 days prior to first dose of LEE011
5. Patients with bone marrow metastatic disease who do not meet the above criteria will be eligible to enroll in the **expansion part** of the study with the following count criteria. These patients will not be evaluable for hematologic toxicity or hematologic DLT.
 - a. ANC $> 750/\mu\text{L}$ within 7 days prior to first dose of LEE011
 - b. Platelet count $> 50,000/\mu\text{L}$ (may receive platelet transfusions) within 7 days prior to first dose of LEE011
 - c. Hemoglobin ≥ 7.5 g/dL (may receive RBC transfusions) within 7 days prior to first dose of LEE011
6. Extent of disease (Refer to [Appendix 1](#), [Appendix 2](#) and [Appendix 3](#)).
 - For the **dose escalation part** of the study patients must have evaluable and/or measurable disease.
 - For the **dose expansion part** of the study patients must have at least one measurable disease as defined by RECIST v1.1. Neuroblastoma patients with positive MIBG (metaiodobenzylguanidine) scan will be eligible and considered evaluable and measurable. Neuroblastoma patients with bone marrow-only disease will NOT be eligible. If palliative XRT has been administered, at least one measurable lesion must not have been irradiated. Previously irradiated lesions must demonstrate clear evidence of progression to be considered measurable.
7. All patients should submit an archival tumor biopsy specimen (collected at diagnosis or relapse). Patients who have no tumor tissue available may be permitted to participate after discussion with Novartis and the investigator.

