10.8 Sample size calculation

Dose-escalation phase

Each cohort will enroll 3 to 6 evaluable patients, including at least six patients at the MTD/RDE level and a minimum of 12 patients in total (details in [Section 6.2.2](#)). Multiple cohorts may be sequentially enrolled to the same dose level. Additional cohorts of 1 to 6 patients may be enrolled at any dose level below the estimated MTD/RDE for further elaboration of safety and pharmacokinetic parameters as required. It is expected that approximately 10 patients may be enrolled and treated within this context. In all, it is anticipated that approximately 28 patients will be treated during the escalation phase for the model to have reasonable operating characteristics relating to its MTD recommendation.

Dose expansion part

During dose expansion a sample size of approximately 18 evaluable patients per arm (including those with MRT or neuroblastoma treated at the recommended MTD/RDE during dose-escalation) will be treated to gain more information about the overall safety and tolerability of LEE011, to provide additional PK and PD data to guide the selection of dosing for future studies with LEE011, and to provide an early opportunity to identify LEE011 anti-tumor activity associated with neuroblastoma and MRT populations.

Assuming no differences in toxicity profile across the subpopulations enrolled in the expansion phase, 36 patients will result in 97% probability of detecting at least one adverse event with a true rate of 10%. This probability rises as the true adverse event rate increases.

To allow for dropouts and expansion of cohorts, it is estimated that approximately 64 patients may be treated in the entire study.

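### Table 14-1 contradicts itself on partial response by MIBG: the words accept any reduction of 50% or more, but the bracket shuts out reductions above 90%

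*Protocol*

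**What the plan says.** Protocol Appendix 2, Table 14-1 defines response for neuroblastoma.

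- **CR** has two listed conditions: complete resolution of non-primary measurable lesions, and "MIBG non-avid (no increased FDG-PET uptake for mIBG non-avid tumors) of non-primary lesions".
- **PR** has two routes joined by an or. The anatomical route is "30% decrease in size/sum of non-primary measurable disease (RECIST), or". The MIBG route asks for 50% or more "reduction in MIBG score (Relative MIBG score ≥ 0.1 to ≤ 0.5", with the bracket closing there.
- **PD** includes any new lesion, growth of more than 20% with at least 5 mm absolute increase, or a relative score of 1.2 or more.
- **SD** is "Neither sufficient shrinkage for MR or PR nor sufficient increase for PD". MR has no row in the table and no definition.

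Protocol Section 10.5.4 plans the response rate with an exact Clopper-Pearson 95% interval by RECIST 1.1, and adds: "The same analysis will also be presented as per RANO in MRT patients and as per INRC in Neuroblastoma patients". Section 10.8 sets the size: "During dose expansion a sample size of approximately 18 evaluable patients per arm". In the inclusion criteria (extent of disease, expansion part), a neuroblastoma patient with a positive MIBG "scan will be eligible and considered evaluable and measurable".

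**The concern.** The bracket looks like a numerical restatement of the words before it, but it is narrower. Its upper end, 0.5, matches a 50% reduction. Its lower end, 0.1, cuts off reductions above 90%, and the CR row does not pick those children up unless avidity has gone and the non-primary measurable lesions have fully resolved. Applied as a range check, the bracket makes the scale non-monotone: a halved score is a response and a nearly cleared one is not.

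What is at stake is the INRC response rate and the INRC response listing. Children whose response rests on MIBG are the exposed group, because the anatomical route may not be open to them. Section 7.2.1 leaves response to the local investigator, and central image collection is for quality checks. Two sites could therefore class the same scan differently, and the table gives them nothing to decide by.

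**Working it through.** No figure in the plan needs reproducing here. The check classifies relative scores under each row of Table 14-1.

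**Inputs.** CR, PR and PD rules: Table 14-1. Arm size of about 18: Protocol Section 10.8. Interval method: Protocol Section 10.5.4.

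**Step 1. Convert.** Reduction = 1 − relative MIBG score.

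| Relative score | Reduction | Words (50% or more) | Bracket (0.1 to 0.5) |
|---|---|---|---|
| 0 | 100% | met | not met |
| 0.01 | 99% | met | not met |
| 0.05 | 95% | met | not met |
| 0.09 | 91% | met | not met |
| 0.10 | 90% | met | met |
| 0.30 | 70% | met | met |
| 0.50 | 50% | met | met |
| 0.51 | 49% | not met | not met |

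Words and bracket agree from 0.1 upward and disagree everywhere below it.

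**Step 2. See who is caught under the bracket reading.** Assume no new lesion and no qualifying growth, so PD does not apply, and less than a 30% decrease in non-primary measurable disease (or none to measure), so the anatomical route to PR does not apply.

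- Score above 0 and below 0.1: still avid, so not CR; below the bracket, so not PR.
- Score 0 with non-primary measurable lesions remaining: the lesions rule out CR, and the score is below the bracket, so not PR.

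In both cases only SD is left, and its wording (too little shrinkage) does not describe a reduction above 90%. The child is SD by default or unclassified.

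**Step 3. See how easily the range is reached.** The protocol gives no MIBG scoring scale. If scores are whole numbers (an assumption), 1/10 = 0.10 is inside the bracket and 1/11 = 0.09 is outside. A baseline of 11 or more with a residual of 1 is then enough. For example, 20 to 1 gives 0.05 (outside) and 20 to 10 gives 0.5 (PR).

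**Step 4. Size the effect on the response rate.** Everyone who meets the bracket also meets the words, so the bracket reading can only remove responders. One child removed from 18 is 1/18 = 5.6 percentage points. With assumed counts:

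- 3/18 = 16.7% (exact 95% CI 3.6 to 41.4)
- 2/18 = 11.1% (exact 95% CI 1.4 to 34.7)

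The documents give no basis for how many children would be affected. With none the change is 0; with two it is 2/18 = 11.1 points.

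**The case against.** The strongest reply is that the bullet's operative criterion is its words. A reader might infer from the bracket that the table makes a child with a reduction above 90% a non-responder and ranks that child below one with a 50% reduction. The documents do not support that as a statement of the rule. A 95% reduction satisfies the words, and the child loses PR only if the bracket overrides them. Nor does any row assign the child to SD. This part of the reply stands: the defect is a contradiction, and misclassification is one possible result of it.

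Four further points also stand as limits.

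- A 30% decrease in non-primary measurable disease gives PR whatever the MIBG score.
- INRC response is a secondary, descriptive measure alongside RECIST, assessed where possible, with no power attached and no bearing on the MTD.
- The SAP (Sections 2.5.4 and 4) reports halted enrollment and restricts analyses to dose escalation, and Section 2.7 plans no secondary efficacy analysis for the final CSR.
- The table's source is described as an unpublished manuscript, and the primary CSR analysis plan is not among the documents. Either might explain the lower bound or settle the classification.

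None of this reconciles the words with the bracket. Within the two documents the reader still has to choose.

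**Conclusion.** The point holds as an internal contradiction in a protocol-defined endpoint. For relative scores below 0.1 without CR, the PR bullet gives opposite answers depending on which half is applied, and nothing else in the protocol or SAP settles it. If the bracket is applied, the INRC response rate can only move down, by 5.6 points per affected child in a planned arm of 18.

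That size rests on three conditions: the bracket governs, the anatomical route is unmet or unavailable, and the arm reaches its planned size. The last no longer describes the study after enrollment was halted, so 1/18 is a design-stage denominator and not an estimate of the effect on reported results. The undefined MR in the SD row is a smaller fault of the same table. The correction is worth making and does not affect the primary objective.

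**What to change.** Make the bracket agree with its words by removing the lower bound. PR by MIBG then becomes a relative score of 0.5 or less in a patient who does not meet CR, stated to include score 0 with residual non-primary measurable lesions. A bracket running from above 0 to 0.5 would not be enough. It would still leave outside both CR and PR a child whose MIBG clears completely while measurable lesions remain and have shrunk by less than 30%.

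In the SD row, define MR or delete it.

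The cost is two table cells, plus the matching line in any INRC derivation that the primary CSR analysis plan may contain. Visits, assessments and data collection do not change. If INRC responses have already been classified, recheck any neuroblastoma patient with a relative score below 0.1 who was not recorded as CR or PR.
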